3.11 Interim Analysis

No interim analyses of efficacy data are planned for this study.

[figure not shown]
4 DATA HANDLING

[figure not shown]
4.1 Derived Endpoints and Data Handling

4.1.1 Handling of Repeated Assessments

If multiple results are reported for an assessment at the same post-baseline visit, then the first record will be used in analysis.

[figure not shown]

[figure not shown]

[figure not shown]

[figure not shown]
4.1.5 Vineland Adaptive Behavior Scales, 3rd Edition

[figure not shown]
The VABS-3 is a standardized psychometric instrument designed to measure personal and social skills needed for everyday living (Sparrow et al., 2005; Sparrow et al., 2016). The VABS-3 is administered via a caregiver using a semi-structured interview format and assesses four main adaptive domains (with associated subdomains): communication (receptive, expressive and written), socialization (interpersonal relationships, play and leisure, coping skills), daily living skills (personal, domestic, community), and motor skills (fine and gross). It also includes a maladaptive behavior scale for identifying behavior problems in individuals ages 3 through adulthood. The scale has been found to have good internal consistency, test-retest reliability and validity (Sparrow et al. 2016). The VABS-3 comprehensive interview form will be used to evaluate subjects on the Communication, Socialization, Daily Living Skills, Motor Skills, and Maladaptive Behavior domains to assess their overall adaptive functioning. QGlobal software will be used to calculate the summary scores. The motor skills domain standard score is calculated only through age 9. Higher scores for regular domain and subdomain scores (Communication, Socialization, Daily Living Skills, Motor Skills and 11 subdomains) indicate better adaptive functioning. Higher scores for maladaptive (internalizing and externalizing scores) indicate more problem behaviors. This assessment is an interview with the caregiver by a trained qualified rater, and for each study site, the same rater is to be used throughout the study.

4.1.7 ABC-Irritability Subscale (ABC-I)

The ABC-I will be used to assess suicidality. The entire ABC-C will be administered although only the ABC-I will be used to assess the potential for self-harm.

The original calculation method includes 5 subscales with the sub scores derivation as follows:

SUBSCALES	Sum of Questions
Irritability	2, 4, 8, 10, 14, 19, 25, 29, 34, 36, 41, 47, 50, 52, 57
Lethargy/Social Withdrawal	3, 5, 12, 16, 20, 23, 26, 30, 32, 37, 40, 42, 43, 53, 55, 58
Stereotypic Behavior	6, 11, 17, 27, 35, 45, 49
Hyperactivity	1, 7, 13, 15, 18, 21, 24, 28, 31, 38, 39, 44, 48, 51, 54, 56
Inappropriate speech	9, 22, 33, 46

For missing data, the following upper limits will apply (number of missing items tolerated for each subscale before discarding the data for that subscale): (I) Irritability (15-item scale): 3 items; (II) Lethargy/Social Withdrawal (16-item scale): 3 items; (III) Stereotypic Behavior (7-item scale) 2 items; (IV) Hyperactivity/Noncompliance (16-item scale): 3 items; (V) Inappropriate Speech (4-item scale): 1 item. If more items than the stated upper limit have been left blank, the subscale will not be computed. If the subscale has the required minimum number of items, the subscale scores will be prorated as follows: (a) Take the total number of items on the subscale and divide this by the number of completed items. This will result in a number larger than 1.00. (b) Multiply that number by the total score for that subscale. (c) This becomes the new total score for this subscale for the given subject.

There is no total score for adding all the subscales together.

4.1.8 Vital Sign Reference Ranges

Reference ranges of vital signs by age group are described in the following table from The Harriet Lane Handbook: A manual for Pediatric House Officers, Twentieth Edition, 2015. A value on the boundary is considered normal; therefore, using the systolic blood pressure example for 2 to 3 years, a value of 105 mmHg would be considered normal, and a value of 106 mmHg abnormal.

Age Group	2 to 3 years	4 to 8 years	9 to 12 years	13+ years
Systolic 95th percentile (mm hg)	Max 105 Min 74	Max 110 Min 78	Max 120 Min 90	Max 129 Min 90
Diastolic 95th percentile (mm hg)	Max 60	Max 70	Max 80	Max 80
Heart rate (beats per min)	80-135	60-130	60-110	60-100
Respiratory Rate (breaths per min)	22-30	18-24	16-22	14-20
ECG (seconds)	PR 0.1-0.14 QRS > 0.07 QTc 0.37-0.44	PR 0.11-0.16 QRS > 0.08 QTc 0.37-0.44	PR 0.12-0.17 QRS > 0.09 QTc 0.37-0.44	PR 0.12-0.20 QRS > 0.10 QTc Males ≤ 0.45, Females ≤ 0.46

4.2 Computation of Derived Data

4.2.1 Time Points and Duration

Standard calculations used across many assessments:

- Changes from baseline = Post Baseline value – Baseline value
- Percentage change from baseline = [(Post Baseline value – Baseline value)/Baseline Value]*100.

4.2.2 Other Data Derivations

Body Mass Index BMI = Weight in Kg / (Height in meter)²

5 PROGRAMMING SPECIFICATIONS

5.1 Analysis Specifications

Sample SAS code for the MMRM ANCOVA analysis is as follows:

```
proc mixed data=temp method=reml;
  class subject visit treat agegrp region;
  model endpoint = visit treat agegrp region baseline
  visit*treat ;
  repeated visit / subject=subject type=covstruc;
  lsmeans visit*treat / diff=all cl alpha=0.05;
run;
```

Use the following sequence for choosing a covariance structure, covstruc.

Use the first covariance structure that converges:

SAS Name for Covariance Structure	Covariance Description
UN	Unstructured
TOEPH	Heterogeneous Toeplitz
ARH(1)	Heterogeneous Autoregressive(1)
CSH	Heterogeneous Compound Symmetry
TOEP	Toeplitz
AR(1)	Autoregressive(1)
CS	Compound Symmetry

If the model converges with an unstructured covariance matrix, the Kenward-Roger approximation will be used to estimate the denominator degrees of freedom. If a structured covariance is used for the model, then a robust sandwich estimator will be utilized for estimating the variance of the treatment effect estimate.

For the MMRM ANOVA model, baseline is excluded from the model statement.

Sample SAS code for the generalized logit model analysis is as follows:

```
PROC GLIMMIX DATA = xxx;
  CLASS subject visit treat agegrp region;
  MODEL endpoint = visit treat agegrp region visit*treat /
  DIST= b link=logit;
  random intercept / subject=subject type = covstruc;
  LSMEANS visit*treat / diff exp cl or;
RUN;
```

Use the sequence for choosing a covariance structure, covstruc, described above with the unstructured covariance replaced by an unstructured Cholesky covariance.

Sample SAS code for the logistic analysis is as follows:

```
PROC LOGISTIC DATA = xxx;  
  CLASS treat agegrp region;  
  MODEL endpoint = treat agegrp region;  
  LSMEANS treat / diff cl or;  
RUN;
```

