7.8.5 Description of Subgroups to be Analyzed

Descriptive statistics will be presented separately by age group (randomization stratification variable: age 4 to 8 years versus age 9 to 12 years) for the primary endpoint and the two key secondary endpoints. Observed values will be reported by treatment group. The difference in means or proportions for OV101 versus placebo groups will also be presented with the corresponding 95% confidence intervals. Similar subgroup analysis will be conducted for region (US versus outside US).

If for a given endpoint, the results in the 2 subgroups appear different from a clinical perspective, the appropriate model (MMRM, GEE, or logistic) could be constructed as described above, including an age-by-treatment interaction term. This interaction term will be tested at alpha level of 0.10 to assess whether the treatment effects are statistically different for the 2 age subgroups.

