3.8.2 Key Secondary Efficacy Endpoint Analyses

A generalized logit model will be used for the analysis of key secondary endpoints: CGI-I-AS response (at least minimally improved) and CGI-I-AS response (at least much improved). The generalized logit models will include the response variable at each visit as the dependent variable, and fixed effects for visit (Week 6 and Week 12), randomized treatment, the visit-by-treatment interaction, age group (randomization stratification variable: age 4 to 8 years versus age 9 to 12 years), and region (randomization stratification variable: US versus outside US). An unstructured Cholesky working correlation for the binary outcome variable will be assumed for the model parameter estimation, and if the model fails to converge, the sequence of covariance structures specified in Section 3.8.1 will be used, until convergence is achieved. If there is no response (at least minimally improved or at least much improved) in either treatment arm at the Week 6 visit, the generalized logit model will be substituted with a logistic regression for the Week 12 CGI-I-AS response variable with effects for the randomized treatment and the two randomization stratification variables. From the model (generalized logit or logistic regression, as appropriate), the Week 12 odds ratio will be presented along with the corresponding 95% confidence interval and 2-sided *P* value.

Descriptive statistics for the observed response (either at least minimally improved or at least much improved) will also be displayed along with the 95% CI based on a

binomial distribution. In addition, the differences in observed percentages between treatment groups will be displayed, along with the corresponding 95% CI for differences in percentages and two-sided p-value.

Sensitivity analyses will be conducted based on method of assessment collection (at least one CGI-I-AS assessment conducted remotely or no CGI-I-AS assessment conducted remotely). Descriptive statistics and a subgroup analysis of the generalized logit analysis described above will be performed.

Additionally, supportive analyses will be performed for the descriptive analysis and generalized logit model with the visit mapping described in section 3.1.8 Table 3 and separately for visit mapping using nominal visits.

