3.8.5 Subgroups to be Analyzed

Descriptive statistics will be presented separately by age group (randomization stratification variable: age 4 to 8 years versus age 9 to 12 years) for the primary and the two key secondary endpoints. Observed values will be reported by treatment group. The difference in means or proportions for OV101 versus placebo will also be presented with the corresponding 95% confidence intervals. Similar subgroup analysis will be conducted for region (US versus outside US).

If for a given endpoint, the results in the two subgroups appear different from a clinical perspective, the appropriate model (MMRM, generalized logit, or logistic) could be constructed as described above, including an age-by-treatment interaction term. This interaction term will be tested at alpha level of 0.100 to assess whether the treatment effects are statistically significantly different for the two age subgroups.

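### The protocol analyses the two alpha-controlled responder endpoints by GEE, but the SAP text and code give a different model, so the test and the kind of odds ratio are not settled

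*SAP*

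**What the plan says.** **Protocol (version 6.0).** The synopsis (Statistical Methods) and 7.8.2 specify GEE for both key secondary endpoints: CGI-I-AS of 1 to 3, and CGI-I-AS of 1 or 2, at Week 12. The fixed effects are visit, treatment, their interaction, age group and region. The working correlation is unstructured, and fallback structures are left to the SAP. For the subgroup model, 7.8.5 again names GEE: "the appropriate model (MMRM, GEE, or logistic) could be constructed".

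**SAP text.** Section 3.8.2 keeps the fixed effects but changes the method: "A generalized logit model will be used for the analysis of key secondary endpoints". It then says "An unstructured Cholesky working correlation for the binary outcome variable will be assumed for the model parameter estimation". Section 3.8.5 follows suit: "the appropriate model (MMRM, generalized logit, or logistic) could be constructed". The visible SAP does not mention GEE.

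**SAP code.** Section 5.1 introduces a PROC GLIMMIX block with "Sample SAS code for the generalized logit model analysis is as follows". The block has a binary distribution, an ordinary logit link and the statement "random intercept / subject=subject type = covstruc". It names no estimation method and no degrees-of-freedom option. The fallback is: "Use the sequence for choosing a covariance structure, covstruc, described above with the unstructured covariance replaced by an unstructured Cholesky covariance".

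**Testing.** Protocol 7.12 and SAP 3.1.3 test both endpoints at two-sided 0.05, in fixed sequence after the primary.

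**Zero responders.** Protocol 7.8.2 and SAP 3.8.2 switch to Week 12 logistic regression when there is no response at Week 6. Neither has a rule for Week 12. SAP 3.8.2 also plans that "the differences in observed percentages between treatment groups will be displayed, along with the corresponding 95% CI for differences in percentages and two-sided p-value", without naming the test.

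**The concern.** One confirmatory hypothesis has three descriptions: GEE in the protocol, a generalized logit with a working correlation in the SAP text, and a random-intercept logistic model in the SAP code. The coded model is not a generalized (multinomial) logit and has no working correlation. GEE and the coded model use different test statistics and can fall on opposite sides of 0.05. Their odds ratios also answer different questions, one about population proportions and one about an individual child. The second responder endpoint is tested only if the first is significant, so a different decision on the first carries forward. If the conflict were resolved after unblinding, the choice could look driven by the result.

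**Working it through.** **1. The fallback list.** A single random intercept per subject has one variance, so its covariance matrix is 1×1. Cholesky, TOEPH, ARH(1), CSH, TOEP, AR(1) and CS then have nothing to structure, and no step changes the model.

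**2. How far apart the two odds ratios are in principle.** The post hoc phase 2 rates in Protocol section 1 are 22.2% (placebo) and 54.5% (OV101 combined). The marginal odds ratio is (0.545/0.455)/(0.222/0.778) = 4.20. Integrating over a normal random intercept, the subject-specific odds ratio that corresponds to these rates is 5.56, 10.20 or 21.24 for an assumed logit-scale SD of 1, 2 or 3. The two are equal only with no between-subject variance or no effect.

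**3. Simulated decisions.** The visible text gives no power for these endpoints, so there is no plan figure to reproduce.

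- From the documents: 45 per arm (SAP 2.2.1), two visits, the model terms, and the phase 2 rates.
- Assumed: 5 per arm missing Week 12 at random; Week 6 rates equal to or two-thirds of Week 12; phi between visits 0.2 to 0.6; age group and region each 50/50 with no effect; the comparison 25% vs 50%.
- GEE: exchangeable correlation (the same as unstructured with two visits), sandwich SE, normal reference.
- SAP code: restricted pseudo-likelihood, taken as the software default, with model-based SE and t reference. Observations are 2 × 90 − 10 = 170, and df = 170 − 92 = 78.
- 2,000 trials per scenario. Zero-cell and non-converged trials are counted as agreeing.

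| Week 12 rates | GEE rejects | SAP code rejects | GEE alone significant |
|---|---|---|---|
| 22.2% vs 54.5% | 85-87% | 77-83% | 4.1-9.8% |
| 25% vs 50% | 64-67% | 53-59% | 5.2-14.0% |
| 38% in both arms (null) | 4.6-5.4% | 2.5-3.4% | not tabulated |

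In the first two rows the code alone was never significant; in a smaller repeat (200 trials per scenario) it was in at most 0.5%. With a normal reference for the code, GEE alone is significant in 2.7-8.5% and 4.0-12.2%. When both tests are calibrated to 5% size at the 38% null, the GEE advantage is −0.6 to 2.7 points.

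For 7.4% vs 20%, 6-14% of trials have a zero cell, so power is not quoted. GEE alone is significant in 4.7-12.7% of all trials.

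**4. Fitted odds ratio at 22.2% vs 54.5%.** The GEE median is 4.4-4.5. The pseudo-likelihood median is 4.5-4.6, 4.9 and 5.5-5.6 at phi 0.2, 0.4 and 0.6. With quadrature (400 trials per scenario) it is 6.5-6.9 at phi 0.2 and 11.9-12.0 at phi 0.4, and GEE alone is significant in 1.0-3.3% and 4.5-4.6% of trials. Quadrature results at phi 0.6 are not reported because too many fits failed.

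**5. Zero responders at Week 12.** At the 7.4% phase 2 placebo rate for at least much improved, P(0 of 40) = 0.926^40 = 4.6% and P(0 of 45) = 0.926^45 = 3.1%. The model odds ratio is then not finite. The planned difference in percentages can still be tested, but the unnamed test matters. For 0/45 vs 5/45, pooled z gives p = 0.021 and Fisher's exact test p = 0.056. For 0/45 vs 10/45 they agree (0.0008 and 0.0011).

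**The case against.** - **No validity problem is shown.** This stands. The coded test is conservative, both endpoints are gated behind the primary, and at equal size the two tests have nearly equal power. With a common normal random intercept, the Week 12 null is also the same under both models.
- **The SAP is consistent in replacing GEE, and generalized logit may be loose naming for a logit-link model.** This is plausible, and nothing shows that the choice was deliberately left open. But the current protocol still says GEE, and the SAP text describes a working correlation that its code does not have.
- **The SAP was written to protocol version 4.0, which is not supplied.** This stands. Only the conflict with version 6.0 is established. A breach of the Protocol 7.1 rule, which asks for an amendment or a justification in the SAP, is not.
- **The quadrature odds ratios come from a method the sample code would not run by default.** This is fair. Under the default the shift is 4.4-4.5 to 4.5-5.6. The quadrature figures show only that the result depends on an unstated option.
- **With two visits a GEE correlation has one parameter, so the fallback list would be inert there too.** This is correct, and it is a reason to replace the list whichever model is chosen.
- **The Week 12 zero-responder gap is a separate matter.** This is also correct. It affects both models and mainly the last endpoint in the sequence.

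**Conclusion.** The concern holds, and the plan should be corrected before unblinding. The conflict is clear from the text and does not depend on the simulation. On the assumptions above, the model choice changes the decision in about 4-10% of trials at the phase 2 rates and 5-14% at 25% vs 50%, always in favour of GEE in the main runs. Most of that reflects conservatism of the coded test. Visit correlation, Week 6 rates and missingness are not given in the documents, so the sizes are indicative. Either model is defensible once it is named and justified.

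**What to change.** Before unblinding, make the protocol and SAP 3.8.2, 3.8.5 and 5.1 name one model:

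- **(a) The protocol's GEE.** Visit repeated within subject, sandwich variance and a population-averaged Week 12 odds ratio. If it does not converge, use an independence working correlation, then Week 12 logistic regression.
- **(b) The random-intercept logistic model.** Call its odds ratio subject-specific, state the estimation method and degrees of freedom, and record the justification or amendment.

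In either case delete the generalized logit label and the inoperative covariance sequence.

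Separately, state which test is confirmatory if an arm has no responders at Week 12. Either designate the percentage difference already planned and name its test, or specify exact or Firth logistic regression.

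The cost is SAP wording and a few lines of sample code, with no effect on data or patients. Option (a) has one drawback: unweighted GEE needs a stronger missing-data assumption than a likelihood mixed model, which would be a legitimate recorded reason for (b). In a check of 1,200 trials per setting, Week 12 was removed for 5 or 9 of 45 OV101 subjects, all Week 6 non-responders, and for as many placebo subjects at random. The GEE median odds ratio moved by at most 0.09 (4.44 to 4.35), with null rejection of 4.2-5.9%.

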5.2 General Specifications

It is suggested that computer-generated table output adhere to the following specifications.

1. Unless otherwise specified, all computer-generated tables and listings should be produced in landscape mode using SAS[®] ODS to create RTF output which can be imported by Microsoft[®] Word in table format. All output should have the following two-line header at the upper left margin:

Ovid Therapeutics Inc.
OV101-19-001

and the following header at the upper right margin:

Page x of y

2. Each table should be identified by in a sequential numeric order, and the table designation should be centered above the title. A decimal system within the numeric numbering (i.e., x.y and x.y.z) should be used to identify tables, listings and figures with related contents. The title is centered in initial capital characters and should include the analysis set analyzed (e.g. SS). The title and table designation are single-spaced, but are separated from the table by at least a double space.

Table No.

First Line of Title
Second Line of Title (if needed)
Analysis Set Analyzed

3. Column headings should be in proper case.
4. For variables with numeric values, include “unit” in column heading when appropriate.
5. Footnotes should be single spaced, but separated by at least a double space from the bottom line of the table. The notes are aligned vertically by the left vertical

border of the table. All output should have at least the footnote about the program name and date of the program run.

```
[1] Footnote 1  
[2] Footnote 2  
[3] Footnote 3
```

```
PROGRAM: program file name
```

```
DDMMYYYY HH:MM
```

6. Unless specified otherwise, all data listings should be sorted by subject number with the study center, and by visit date within subject, where appropriate.
7. For tables that summarize categorical (discrete) data, a Missing category should be added to any parameters for which information is not available for any subject.
8. Unless otherwise specified, the estimated mean, median, first and third quartiles (Q1 and Q3, respectively) for a set of values should be printed out to one more decimal place than the raw (observed) data and rounded appropriately. Standard errors (or standard deviations) should be printed out to two additional decimal places than the raw (observed) data and rounded appropriately. For example, for age (with raw data in whole years):

n	xx
Mean (SD)	xx.x (xx.xx)
Median	xx.x
Q1, Q3	xx.x, xx.x
Min, Max	xx, xx

9. The p-values will be printed in the tables rounded appropriately to 4 decimal places and formatted as '0.xxxx'. P-values less than 0.0001 will be formatted in the tables as '<0.0001'.
10. All fractional numeric values should be printed with a zero to the left of the decimal point (e.g., 0.12, 0.3).
11. Unless otherwise specified, percentage values should be printed with one digit to the right of the decimal point (e.g., 12.8, 5.4).
12. Missing descriptive statistics due to non-estimability in tables, as well as missing data in subject listings should be represented as either a hyphen (“-“) with a corresponding footnote (“ - = unknown or not evaluated”), or as “N/A” with the footnote “N/A = not applicable” whichever is appropriate.
13. Dates printed as a result in the table, listing, or graph should be printed in SAS DATE9. format (“DDMONYYYY”: 01 JUL 2002). Missing portions of dates should be represented on subject listings as dashes (-- JUL 1999). Dates that are missing because they are not applicable for the subject should be listed as “N/A”, unless otherwise specified.

